Endpoints and variables

The primary endpoint in group I (boys with absent puberty) will be increase in blood LH after GnRH test. Testis size ≥ 8 mL will be the primary endpoint for group II (boys with delayed puberty).

Secondary endpoints are increase in testis size from baseline to 1 year (group I), serum testosterone levels during treatment with Testoviron Depot® and Nebido®, signs of masculinization from baseline to 3, 6 and 12 months, body growth, hair growth measured as tanner stage and inspection of axillaries hair, deepening of voice, gender identity and health-related quality of life.

TABLE OF CONTENTS	PAGE
PROTOCOL SYNOPSIS	2
TABLE OF CONTENTS	4
LIST OF ABBREVIATIONS AND DEFINITION OF TERMS.....	7
1. INTRODUCTION	9
1.1 Background	9
1.2 Rationale for conducting this study	10
1.3 Research hypothesis.....	11
1.4 Benefit/risk and ethical assessment.....	11
1.5 Ethical assessment	11
2. STUDY OBJECTIVES AND ENDPOINTS.....	12
2.1 Primary objective	12
2.1.1 Primary endpoint(s)	12
2.2 Secondary objective(s).....	12
2.3 Exploratory variables	12
3. STUDY DESIGN AND PROCEDURES	12
3.1 Overall study design and flow chart	12
3.1.1 Stopping criteria.....	15
3.1.1.1 Stopping criteria for dose continuation.....	15
3.2 Rationale for study design, doses and control groups.....	15
4. SUBJECT POPULATION.....	16
4.1 Inclusion criteria Group I (absent puberty).....	16
4.2 Inclusion criteria Group II (delayed puberty)	17
4.3 Exclusion criteria	17
4.4 Subject enrolment and randomization	18
4.5 Restrictions during the study	18
4.6 Withdrawal of subjects and study stop	18
4.6.1 Premature termination of the study.....	18
5. TREATMENTS	19
5.1.1 Doses and treatment regimens	19
5.1.2 Labelling	20
5.1.3 Storage	20
5.2 Concomitant medication and post-study treatment(s)	20

5.3	Treatment compliance.....	20
5.3.1	Accountability.....	21
6.	STUDY MEASUREMENTS AND VARIABLES	21
6.1	Screening and demography.....	21
6.1.1	Methods of assessments.....	21
6.1.2	Post-study.....	21
6.2	Bone age.....	22
6.3	LHRH-test.....	22
6.4	Pubertal stage.....	22
6.5	Signs of masculinization	22
6.6	Blood sampling.....	22
6.6.1	Study-specific blood samples	22
6.6.1.1	Haemoglobin (Hb)	23
6.6.1.2	LH and FSH	23
6.6.1.3	DHEAS	23
6.6.1.4	Testosterone and Estrogen.....	23
6.6.1.5	SHBG, AMH, InhibinB	23
6.6.1.6	Mass spectrometric analysis of steroids.....	23
6.6.2	Questionnaires.....	23
6.6.2.1	Standardize procedures for administration of questionnaires.....	23
6.6.2.2	KIDSCREEN	24
6.6.2.3	Jag Tycker Jag Är	24

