2.2 Secondary objective(s)

- Testis size (mL) in group I from baseline to 1 year (group I)
- Serum testosterone levels during treatment with Testoviron Depot® and Nebido®.
- Signs of masculinization from baseline to 3, 6 and 12 months (Body growth, hair growth measured as tanner stage and inspection of axillaries hair, deepening of voice, gender identity)
- Health-related Quality of life (KIDSCREEN, JTJÄ)

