4.1 Inclusion criteria Group I (absent puberty)

For inclusion in the study subjects must fulfil the following criteria.

1. Signed informed consent

2. Healthy young male subjects 14-16 years old
3. Morning serum testosterone value by inclusion (07.30-09.00) and start (08.00-10.00) that is less 0.5 nmol/L
4. Pre-pubertal LHRH test
5. Testicular volume 1-3ml bilaterally
6. Bone age 11 years or older
7. Otherwise clinically normal physical findings and laboratory values as judged by the investigator

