6. STUDY MEASUREMENTS AND VARIABLES

6.1 Screening and demography

Each subject will undergo a pre-entry medical examination 5-14 days prior to the first study day. This will consist of:

- Information and signed consent
- Demographic data - date of birth, birth weight and length, current height and weight,
- Habits of nicotine
- Past and present medical including family history
- Present medications
- Pulse, systolic and diastolic blood pressure
- Physical examination including cardiovascular and respiratory systems, abdomen, general appearance, skin, head and neck, lymph nodes, thyroid and reflexes and specification of abnormalities
- Bone age
- Health-related quality of life (KIDSCREEN, JTJÄ)
- Blood sampling (20 ml) for haematology assessments and clinical chemistry (Table 4)
- Puberty stage (testicular volume and pubic hairiness)

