For young males with absence or delayed progress of puberty, the number of subjects (n=30 in Group I and n=40 in Group II) in a parallel-group designed study is considered sufficient for judgments on the primary hypothesis due to clinical experience of treating the present study population with hormone therapy. However, to not expose boys for a new treatment (Nebido and Puregon in group I and Nebido in group II) that is inferior to SoC, a futility test will be performed after 10 evaluable patients in each arm in the groups. This futility analysis can result in stopping the study if the new treatment (Nebido and Puregon in group I and Nebido in group II) is statistically significant inferior or superior, or

continue the study as planned or increase the numbers patients to have a possibility to reach statistical significance.

The primary objective will be studied with non parametric methods Fisher exact chi-square test,

Descriptive statistics, parametric and non parametric tests will be used for the secondary objectives.

Other statistical methods e.g. regression modelling might be used in an exploratory fashion but no formal interference will be made.

Demographics, safety and self-assessed outcomes will be presented by means of descriptive statistics.

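### Section 8 plans no baseline-adjusted comparison for the continuous secondary endpoints, and treats quality of life inconsistently

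*SAP*

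**What the plan says.** Three sentences in section 8 govern everything beyond the primary endpoints.

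- Secondary objectives: "Descriptive statistics, parametric and non parametric tests will be used for the secondary objectives". No test is named and no covariate is mentioned.
- Modelling: "Other statistical methods e.g. regression modelling might be used in an exploratory fashion but no formal interference will be made". I read the last noun as inference.
- Self-assessed outcomes: "Demographics, safety and self-assessed outcomes will be presented by means of descriptive statistics".

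The endpoints themselves are defined elsewhere. The synopsis gives Group I testis size as "increase in testis size from baseline to 1 year (group I"), and section 2.2 repeats this. Section 2.2 also lists "Signs of masculinization from baseline to 3, 6 and 12 months (Body growth, hair growth measured as tanner stage and inspection of axillaries hair"), so body growth is a change from baseline too. Quality of life (KIDSCREEN and JTJÄ) is a secondary objective in section 2.2, with no reference to baseline.

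All the baselines exist. Section 6.1 and Table 1 put height, weight, testicular volume and both questionnaires at visit 1. Table 1 repeats height, weight and pubertal stage at 3, 6 and 12 months, and the questionnaires at 6 and 12 months.

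**The concern.** The trial has 15 boys per arm in Group I and 20 per arm in Group II, and section 4.4 mentions no stratification. In arms this small, chance differences at baseline are common and not negligible. A comparison of raw follow-up values carries part of such a difference into the apparent treatment effect. A comparison of change scores subtracts all of it, which is too much unless baseline and follow-up are almost perfectly correlated. A linear model of the follow-up value on arm and baseline takes out the right share, and it is usually the more precise of the three. Section 8 leaves that model outside inference while letting unspecified tests in.

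Two further things are left open. The plan does not say whether a secondary comparison uses raw values or change where the endpoint wording is silent, or whether the test is parametric. The study is open (section 3.2) and the investigators do the analysis (section 9.1), so a rule written in advance has value. For quality of life, a reader cannot tell whether any between-arm comparison is planned.

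**Working it through.** **The plan's own figure.** The only calculation in the document is Appendix E, which concerns the primary endpoint. With 16/20 successes in both arms, the standard error is √(0.008 + 0.008) = 0.126491, and the lower limit is 0 − 1.96 × 0.126491 = −0.248, inside −0.25. With 15/20 on the new drug, it is −0.05 − 1.96 × 0.131814 = −0.308, outside. The stated requirement of 16 successes reproduces. It has no bearing on the secondary endpoints, for which the plan gives no figure.

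**Inputs.** Arm sizes n = 15 and 20 (Table 2). Assumed, because the plan gives none: a true difference of 0.8 SD, baseline–follow-up correlation ρ from 0.3 to 0.8, normal data with the same SD at both times, and two-sided 5% tests.

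**Chance imbalance.** The standard error of the baseline difference in SD units is √(2/n): √(2/15) = 0.365 and √(2/20) = 0.316. The probability that it exceeds 0.5 SD in either direction is 2[1 − Φ(0.5/0.365)] = 0.171 and 2[1 − Φ(0.5/0.316)] = 0.114.

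**Effect of an imbalance d on the estimate.** Raw values: ρd. Change scores: (ρ − 1)d. Adjusted: 0 in expectation. For d = 0.5 SD:
- ρ = 0.5: raw +0.25 SD, change −0.25 SD.
- ρ = 0.8: raw +0.40 SD, change −0.10 SD.

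**Power.** With N = 2n, the variances in SD² are 1 (raw), 2(1 − ρ) (change) and (1 − ρ²)(1 + 1/(N − 5)) (adjusted). The noncentrality is 0.8/√(2V/n), with N − 2 degrees of freedom for the tests and N − 3 for the model. Example at n = 15, ρ = 0.5: the adjusted variance is 0.75 × 1.04 = 0.78, so the noncentrality is 0.8/√(0.78 × 2/15) = 2.48, against 0.8/√(2/15) = 2.19 for raw or change.

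| n per arm | ρ | Raw | Change | Adjusted |
|---|---|---|---|---|
| 15 | 0.3 | 56.2% | 43.2% | 58.4% |
| 15 | 0.5 | 56.2% | 56.2% | 66.7% |
| 15 | 0.7 | 56.2% | 77.9% | 82.6% |
| 15 | 0.8 | 56.2% | 91.7% | 93.2% |
| 20 | 0.3 | 69.3% | 54.9% | 72.1% |
| 20 | 0.5 | 69.3% | 69.3% | 80.1% |
| 20 | 0.7 | 69.3% | 88.9% | 92.5% |
| 20 | 0.8 | 69.3% | 97.4% | 98.2% |

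At ρ = 0.5 the gain over either alternative is 66.7 − 56.2 = 10.5 points with 15 per arm. At 0.3 the gain over raw values is 2.2 points (n = 15) or 2.8 (n = 20). At 0.8 the gain over change scores is 1.5 points (n = 15). If the correlation were zero, adjustment would lose a little to raw values: 54.4% against 56.2% at n = 15. The difference detectable with 80% power at n = 15, ρ = 0.5 is 1.06 SD for raw or change and 0.94 SD adjusted.

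**Quality of life.** Section 2.2 makes it a secondary objective, so the tests sentence of section 8 applies. It is also self-assessed, so the descriptive sentence applies. The two give different answers and neither refers to the other.

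**The case against.** A reader might infer that the plan throws the baseline away. The documents do not support that for Group I testis size or body growth: both are defined from baseline, so the baseline enters by subtraction, and the raw column above is not their planned comparator. Nor does the text say that the tests are unadjusted. It leaves them unspecified, and an analysis of covariance is a parametric method. The sentence on regression makes that reading unlikely but does not exclude it. It would also be too strong to say that quality of life has no between-arm comparison, because one of two conflicting sentences provides for tests.

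A reader might also infer that unadjusted tests give too many false positives. They do not: over repeated randomisation they keep their 5% level, and chance imbalance is already in their standard errors.

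The plan has a defence as well. It calls the study hypothesis-generating and has no power calculation, and these endpoints are secondary. Keeping models exploratory is a tenable position. For Group I testis size, the entry criterion "Testicular volume 1-3ml bilaterally" limits absolute imbalance and fits poorly with the equal-SD normal model used above, so the table is least reliable there.

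These points stand and limit the finding. They do not explain why an unspecified test may be reported as inference while the same comparison with baseline in the model may not.

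**Conclusion.** The point holds in a limited form. No baseline-adjusted comparison is planned for the continuous secondary endpoints, although every baseline needed is collected, and section 8 is inconsistent on quality of life. What is lost is precision and protection against conditional bias, with no effect on error control or on the primary endpoints. The size is uncertain: about 10 power points at correlation 0.5, and only 1.5 to 3 points against the better unadjusted alternative at 0.3 or 0.8. These figures rest on an assumed 0.8 SD difference, assumed correlations and equal SDs at both times, none of which the plan states. The imbalance probabilities of 17% and 11% need only the arm sizes and a normal approximation. This is an inexpensive improvement to a secondary analysis plus one inconsistency to resolve.

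**What to change.** In section 8, add a rule for the continuous secondary endpoints. Report the between-arm difference with a 95% confidence interval from a linear model of the follow-up value on arm and visit 1 value, fitted separately in Groups I and II, for:

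- Group I testis size at 12 months;
- height and weight at 3, 6 and 12 months;
- KIDSCREEN and JTJÄ scores at 6 and 12 months.

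Keep the descriptive tables beside it. Amend the regression sentence so that it does not exclude this model, and reconcile the two sentences that cover quality of life.

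Label the results secondary and not adjusted for multiplicity. The rule yields 1 + (2 × 3 × 2) + (2 × 2 × 2) = 21 intervals if each questionnaire gives one score, and more if KIDSCREEN domains are reported separately, so the label matters.

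The cost is a few lines of text and one degree of freedom per model, in the software already named in section 9.1. No new data, visits or patients are needed.

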8.1.1 Evaluation and calculations of variables

In Group I: For the boys with absent puberty we need to follow the testosterone values to evaluate the doses given. We also need to follow estrogen since testosterone is converted into estrogen and then terminate the growth spurt. This will give us new information on how to better induce puberty

9. DATA MANAGEMENT

9.1 Recording of data

Paper case record forms (CRF), will be used to record all data. Data entry, editing and analyses will be done by the responsible investigators and study nurse(s). The investigators will ensure that all data collected in the study will be provided. He/she ensures the accuracy, completeness, legibility and timeliness of the data recorded in the appropriate sections of the CRF and according to any instructions provided.

Clean File/database lock must be documented. The reason for any excluded data or protocol deviations will be described in the study report. Any changes in the database after Clean File/database lock must be documented.

Data will thereafter be entered into an Excel datasheet and analysed with S.P.S.S.19 statistical software.

CRF documentation and other source data will be retained for at least 10 years after finalization of the clinical study.

9.1.1 Source data

All patient source data such as analysis results from the hospital laboratories and other measurements made will be stored at the hospital according to routines.

The CRFs serves as the source for demographic data, medical history and physical examination and measurements. Original scorings of patient-reported outcomes (x) and xx analysis reports will be defined as source data.

9.2 Training of study site personnel

The local investigator at each site will ensure that appropriate training relevant to the study is given to all of these staff and that any new information relevant to the performance of this study is forwarded to the staff involved. All staff has undergone GCP training.

9.3 Monitoring of the study

An independent study nurse will be appointed for monitoring the study. The monitor will be appropriately trained and informed about the nature of the study, patient written information, GCP and applicable regulatory requirements. Monitor's qualifications will be documented.

The monitor will have regular contacts with the study sites to verify informed consents of participating subjects, to confirm that facilities remain acceptable, that the investigational team is adhering to the protocol that data are being accurately recorded in the Case Report Forms (CRF) and that therapy accountability is being carried out. The study nurse will also ensure source data verification (comparison of the data in the CRF with the hospital/practice and other records at the investigational site).

9.4 Study agreements

All agreements between the Principal Investigator and laboratory or other technical facilities in which the measurement or assessment of the study evaluation criteria are performed must be in place before any study-related procedures can take place, or subjects be enrolled.

9.5 Changes to the protocol and informed consent form

If there are any substantial changes to the study protocol, then these changes will be documented in a study protocol amendment anywhere required a new version of the study protocol (Amended Protocol).

The amendment must be approved by the Ethics Committee and if applicable, also the national regulatory authority, before implementation.

If a protocol amendment requires a change to the Informed Consent Form, the Ethics Committee must approve the revised Informed Consent Form before the revised form is used.

9.6 Insurances

Like in the general Swedish health care, the study subjects are covered by the Patient insurance and pharmaceutical insurance.

9.7 Rapport and publications

A summary report of study results will be sent to the Ethics Committee and the MPA within one year after entire study is finalized.

Results from the study may be published in national and international scientific journals.

10. STUDY TIMETABLE

First Subject In: March 2013. Last Subject Last Visit: December 2015 (group II) and December 2022 (group I)

Final Study Report: December 2016 or within 12 months from end of study.

10.1 Definition of end of study

The end of the entire study is defined as "the last visit of the last subject undergoing the trial".

It is important to distinguish between Serious Adverse Events (SAEs) and severe adverse events (AEs). Severity is a measure of intensity whereas seriousness is defined by the criteria listed below. An AE of severe intensity need not necessarily be considered serious. For example, nausea which persists for several hours may be considered severe nausea, but not an SAE. On the other hand, a stroke which results in only a limited degree of disability may be considered a mild stroke but would be a SAE.

A medical emergency usually constitutes an SAE and is to be reported as such

A serious adverse event is an AE occurring during any study phase (i.e. run-in, pre-entry, screening, treatment, wash-out, follow-up), and at any dose of the investigational product, comparator or placebo, that fulfils one or more of the following criteria:

- results in death
- is immediately life-threatening
- requires in-patient hospitalisation or prolongation of existing hospitalisation
- results in persistent or significant disability or incapacity
- is a congenital abnormality or birth defect

- is an important medical event that may jeopardise the subject or may require medical intervention to prevent one of the outcomes listed above.

For reporting purposes, any suspected transmission via a medicinal product of an infectious agent is also considered an SAE and is reported in an expedited manner. Any organism, virus or infectious particle (for example prion protein transmitting Transmissible Spongiform Encephalopathy), pathogenic or non-pathogenic, is considered an infectious agent.

Definitions for severity rating

0. None – No symptoms
1. Mild - Transient symptoms; awareness of sign or symptom, but easily tolerated. No interference with the subject's daily activities
2. Moderate - Marked symptoms; discomfort sufficient to cause interference with normal activities. Moderate interference with the subject's daily activities
3. Severe - Considerable interference with the subject's daily activities; unacceptable, incapacitating. Inability to perform normal activities

N/A Not Applicable

Causal relationship

The causality of (S)AEs (ie, their relationship to study treatment and/or the investigational procedure) will be assessed by the investigator(s), who in completing the relevant case report form must answer "yes" or "no" to the question "Do you consider that there is a reasonable possibility that the event may have been caused by the drug/the investigational procedure?"

The following terms and definitions are used when assessing the causal relationship between each AE and the relevant trial product(s):

1. Definite - There is no doubt that the incident is related
2. Probable - Good reason and sufficient documentation to assume a causal relationship
3. Possible- A causal relationship is conceivable and cannot be dismissed
4. Unlikely - The event is most likely related to aetiology other than the trial product
5. Not related – The event is not related to the trial product
6. Unknown/Unclassifiable: a report suggesting an adverse event reaction, which cannot be judged because information is insufficient or contradictory and which cannot be supplemented or verified.

N/A Not Applicable

Causal relationship in cases where the disease under study has deteriorated due to lack of effect will be classified as no reasonable possibility.

For SAEs causal relationship will also be assessed for additional study drug and/or other medication and/or study procedure. Note that for SAEs that could be associated with any study procedure the causal relationship is implied as “yes”.

Action taken:

- 0 None
- 1 Dose of study drug changed
- 2 Study drug temporarily stopped
- 3 Study drug stopped
- N/A Not Applicable

Reporting in the Case report Form

The following variables will be recorded in the CRF for each AE; description of the AE, the date and time when the AE started and stopped, maximum intensity, whether the AE is serious or not, causality rating (yes or no; if yes specify), action taken with regard to investigational product, AE caused subject to discontinue study and outcome.

Adverse Events based on signs and symptoms

All AEs spontaneously reported by the subject or reported in response to the open question from the study personnel: “*Have you had any health problems since the previous visit?*”, or revealed by observation will be collected and recorded in the CRF. When collecting AEs the recording of diagnoses is preferred (when possible) to recording a list of signs and symptoms. However, if a diagnosis is known and there are other signs or symptoms that are not generally part of the diagnosis, the diagnosis and each sign or symptom will be recorded separately.

Follow-up – Outcome assessment

Any AEs that are unresolved at the patient’s last AE assessment in the study are followed up by the investigator for as long as medically indicated, but without further recording in the CRF.

The following terms and definitions are used in assessing the final outcome of an AE:

- Recovered - The subject has fully recovered, or by medical or surgical treatment the condition has returned to the level observed at the first trial-related activity after the subject signed the informed consent.

- Recovering - This term is only applicable if the subject has completed the trial or has died from another AE. The condition is improving and the subject is expected to recover from the event.
- Recovered with sequelae - The subject has recovered from the condition, but with lasting effect due to a disease, injury, treatment or procedure. If a sequela meets an SAE criterion, the AE must be reported as an SAE.
- Not recovered - The condition of the subject has not improved and the symptoms are unchanged, or the outcome is not known at the time of reporting.
- Fatal - This term is only applicable if the subject died from a condition related to the reported AE. Outcomes of other reported AEs in a subject before he/she died should be assessed as “recovered”, “recovering”, “recovered with sequelae” or “not recovered”. An AE with fatal outcome must be reported as an SAE.
- Unknown - This term is only applicable if the subject is lost to follow-up

Reporting of serious adverse events

For studies in countries implementing the EU Clinical Trials Directive, informing Ethics Committees and Regulatory Authorities will be performed by the sponsor.

All Suspected Unexpected Serious Adverse Reactions (SUSARs) have to be reported, whether or not considered causally related to the investigational product, or to the study procedure(s). The Clinical Study Serious Adverse Event Report Form will be used together with other relevant supporting documentation (e.g. ECG, laboratory results, autopsy report) and relevant CRF modules. All SUSARs have to be electronically registered in the EMEAs database.

FURTHER GUIDELINES ON THE DEFINITION OF A SERIOUS ADVERSE EVENT

Life threatening

‘Life-threatening’ means that the subject was at immediate risk of death from the AE as it occurred or it is suspected that use or continued use of the product would result in the subject’s death. ‘Life-threatening’ does not mean that had an AE occurred in a more severe form it might have caused death (eg, hepatitis that resolved without hepatic failure).

Hospitalisation

Out-patient treatment in an emergency room is not in itself a serious AE, although the reasons for it may be (eg, bronchospasm, laryngeal oedema). Hospital admissions and/or surgical operations planned before or during a study are not considered AEs if the illness or disease

existed before the subject was enrolled in the study, provided that it did not deteriorate in an unexpected way during the study.

Important medical event or medical intervention

Medical and scientific judgement should be exercised in deciding whether a case is serious in situations where important medical events may not be immediately life-threatening or result in death, hospitalisation, disability or incapacity but may jeopardize the subject or may require medical intervention to prevent one or more outcomes listed in the definition of serious. These should usually be considered as serious.

Examples of such events are:

- *Angioedema not severe enough to require intubation but requiring iv hydrocortisone treatment*
- *Hepatotoxicity caused by paracetamol (acetaminophen) overdose requiring treatment with N-acetylcysteine*
- *Intensive treatment in an emergency room or at home for allergic bronchospasm*
- *Blood dyscrasias (eg, neutropenia or anaemia requiring blood transfusion, etc) or convulsions that do not result in hospitalisation*
- *Development of drug dependency or drug abuse*

A guide to interpreting the causality QUESTION

The following factors should be considered when deciding if there is a “reasonable possibility” that an AE may have been caused by the drug.

- Time Course. Exposure to suspect drug. Has the subject actually received the suspect drug? Did the AE occur in a reasonable temporal relationship to the administration of the suspect drug?
- Consistency with known drug profile. Was the AE consistent with the previous knowledge of the suspect drug (pharmacology and toxicology) or drugs of the same pharmacological class? OR could the AE be anticipated from its pharmacological properties?
- Dechallenge experience. Did the AE resolve or improve on stopping or reducing the dose of the suspect drug?
- No alternative cause. The AE cannot be reasonably explained by aetiology such as the underlying disease, other drugs, other host or environmental factors.

- Rechallenge experience. Did the AE reoccur if the suspected drug was reintroduced after having been stopped? A re-challenge would not normally be recommended or supported.
- Laboratory tests. A specific laboratory investigation (if performed) has confirmed the relationship?

A “reasonable possibility” could be considered to exist for an AE where one or more of these factors exist.

In contrast, there would not be a “reasonable possibility” of causality if none of the above criteria apply or where there is evidence of exposure and a reasonable time course but any dechallenge (if performed) is negative or ambiguous or there is another more likely cause of the AE.

In difficult cases, other factors could be considered such as:

- Is this a recognised feature of overdose of the drug?
- Is there a known mechanism?

Ambiguous cases should be considered as being a “reasonable possibility” of a causal relationship unless further evidence becomes available to refute this. Causal relationship in cases where the disease under study has deteriorated due to lack of effect should be classified as no reasonable possibility.

Other significant Adverse Events

An expert will identify other significant Adverse Events (OAEs) during the evaluation of safety data for the Clinical Study Report. Significant adverse events of particular clinical importance, other than SAEs and those AEs leading to discontinuation of the subject from study treatment, will be classified as OAEs. Examples of these are marked haematological and other laboratory abnormalities, and certain events that lead to intervention (other than those already classified as serious), dose reduction or significant additional treatment. For each OAE, a narrative will be written and included in the Clinical Study Report.

Procedures in case of pregnancy

Pregnancy itself is not regarded as an adverse event unless there is a suspicion that the investigational product under study may have interfered with the effectiveness of a contraceptive medication. The outcome of all pregnancies (spontaneous miscarriage, elective termination, normal birth or congenital abnormality) must be followed up and documented even if the subject was discontinued from the study. All reports of congenital abnormalities/birth defects are SAEs. Spontaneous miscarriages should also be reported and

handled as SAEs. Elective abortions without complications should not be handled as AEs. All outcomes of pregnancy must be reported to PI on the pregnancy outcomes report form.

Part I of this form must be completed in full and returned to PI within 30 days. Part II of the form must be completed when the outcome of the pregnancy is known. Reports of normal outcomes should be sent within 30 days.

Overdose

- An overdose with associated AEs is recorded as the AE diagnosis/symptoms on the relevant AE modules in the CRF.

Study protocol Appendix C – Ethics and regulatory review

The final study protocol, including the final version of the Written Informed Consent Form and other information given to subjects eg, advertisements must be approved or given a favourable opinion by an Ethics Committee before enrolment of any subject into the study.

Before enrolment of any subject into the study, the final study protocol, including the final version of the Informed Consent Form, is approved by the national regulatory authority or a notification to the national regulatory authority is done, according to local regulations.

It is the responsibility of the Principal Investigator to apply to the Ethics Committee in writing. The application document should:

- contain the name and address of the Ethics Committee
- clearly identify, by title and date, the protocol and other documents submitted for review
- be dated.

In addition, the Principal Investigator should request the Ethics Committee to provide:

- their approval/opinion in a dated document identifying the Principal Investigator's application
- Ethics Committee composition for the meeting when the approval was given
- a statement confirming that the Ethics Committee is organised and operates according to GCP and applicable laws and regulations.

The Principal Investigator is responsible for informing the Ethics Committee of any modifications and amendments to the protocol as per local requirements.

Progress reports and notifications of serious and unexpected adverse drug reactions will be provided to the Ethics Committee according to local regulations and guidelines

All correspondence with the Ethics Committee should be filed by the Principal Investigator in the ISF.

The Principle Investigator is also responsible for obtaining approvals from scientific bodies (eg, to use radiolabelled substances) if necessary for the study.

SUBJECT INFORMATION AND WRITTEN INFORMED CONSENT FORM

The Principal Investigator(s) at each centre will ensure that the subject is given full and adequate oral and written information about the nature, purpose, possible risk and benefit of the study. Subjects must also be notified that they are free to discontinue from the study at any time. The subject should be given the opportunity to ask questions and allowed time to consider the information provided.

The subject's signed and dated informed consent must be obtained before conducting any procedure specifically for the study.

The Principal Investigator(s) must store the original, signed Informed Consent Form in the Investigator's Study File. A copy of the signed Informed Consent Form must be given to the subject.

If a protocol amendment requires a change to the Informed Consent Form, the Ethics Committee must approve modifications that lead to a revised Informed Consent Form before the revised form is used.

SUBJECT DATA PROTECTION

The Informed Consent Form will incorporate (or, in some cases, be accompanied by a separate document incorporating) wording that complies with relevant data protection and privacy legislation.

Extra precautions are taken to preserve confidentiality and prevent genetic or other study data being linked to the identity of the subject. In exceptional circumstances, however, certain individuals might see both the genetic, other study data and the personal identifiers of a subject. For example, in the case of a medical emergency or an investigator might know a subject's identity and also have access to his or her data. Also Regulatory authorities may require access to the relevant files, though the subject's medical information and the genetic files would remain physically separate

AUDITS AND INSPECTIONS

Authorized representatives of Sponsor, a regulatory authority, or an Ethics Committee may perform audits or inspections at the centre, including source data verification. The purpose of an audit or inspection is to systematically and independently examine all study-related activities and documents, to determine whether these activities were conducted, and data were recorded, analysed, and accurately reported according to the protocol, Good Clinical Practice (GCP), guidelines of the International Conference on Harmonisation (ICH), and any applicable regulatory requirements.

Study protocol Appendix D - Dose adjustment of Puragon and Nebido

I) Boys with absence of puberty

- a. The rhFSH (Puregon®) dose will be adjusted to reach serum FSH levels of 3.0 IU/mL or higher. The starting dose will be 50 IU. The FSH levels will be determined on visit 4. If serum FSH is lower than 3.0 IU/L the dose will be increased to 75 IU. If serum FSH are higher than 5.0 IU/L the dose will be reduced to 30 IU. Patients who have changed the Puregon® to 30IU or 75IU, an extra visit 7 -10 days after the change will be done to determine the serum FSH levels. For patients on 75IU Puregon® if serum FSH under 3.0 IU/L the Puregon® dose will be increased to 100IU and if serum FSH are higher than 5.0 the dose will be reduced to 50IU. For patients on 30IU Puregon® if serum FSH under 3.0 IU/L the Puregon® dose will be increased to 50IU and if serum FSH are higher than 5.0 the treatment with Puregon® will be stopped. If serum FSH in these patients are not 3.0 IU/mL or higher at visit 5, the patient will be taken out from the study.
- b. Dose adjustments of starting dos of Puregon® is possible after the first 5 patients for the rest of the study. If the serum FSH levels are less than 3.0 IU/L at visit 4 in 3 or more of 5 patient, the starting dose will be increased to 75IU for the remaining patients randomized to Puregon® and Nebido®.
- c. Boys who have been randomized to Puregon®/Nebido but at inclusion have serum levels of FSH above 3 will not be treated with Puregon®, but if the patient during the study on 2 concomitant visits have serum FSH below 3.0 IU/L will be treated with (Puregon®) as described above
- d. The Nebido treatment will be dose adjusted in patients after the first injection if the testosterone profile shows to high or low levels, the goal is to have the similar levels during 2 months as in early puberty (1-3 nM). If the serum testosterone level are less than 1.0 nM at visit 6, the dose will be increased to 250mg for the remaining part of the study. If the serum testosterone level is higher than 3.0 nM at visit 6, the dose will be decreased to 150mg.

II Boys with delayed/slow progress of puberty

- a. Dose adjustments of Nebido® is possible after the first 5 patients on Nebido® (250 mg) for the rest of the study. The aim for the Nebido® treatment is to have testosterone levels in the lower range of mid puberty (4-9 nmol/L) during 2 months. An interim analysis will be done after the first 5 patients and thereafter keep or adjust the dose for the remaining study. If the serum testosterone level are less than 4.0 nM at visit 6 in 3 or more of 5 patient, the dose will be increased

to 300 mg for the remaining patients randomized to Nebido®. If the serum testosterone level are higher than 9.0 nM at visit Y in 2 or more in 5 patient, the dose will be decreased to 200 mg for the remaining patients randomized to Nebido®.

Study protocol Appendix E - Statistiska beräkningar

p2	nOK, gl drog	nOK, ny drog	p1		p1-p2	$p1*(1-p1)/n1$	$p2*(1-p2)/20$	under rot	rot
0,8	16	17	0,85		0,05	0,006375	0,008	0,014375	0,119896
0,8	16	16	0,8		0	0,008	0,008	0,016	0,126491
0,8	16	15	0,75		-0,05	0,009375	0,008	0,017375	0,131814
0,8	16	14	0,7		-0,1	0,0105	0,008	0,0185	0,136015
0,8	16	13	0,65		-0,15	0,011375	0,008	0,019375	0,139194
0,8	16	12	0,6		-0,2	0,012	0,008	0,02	0,141421

p2 %"lyckade" i testoviron gruppen
 p1 %"lyckade" i grupp med ny behandling

16 pojkar måste "lyckas" i den nya behandlingen, dvs lika många som antas "lyckas" efter den gamla behandlingen för inte den nya behandlingen ska betraktas som inferior, dvs 25% färre lyckade med nya drogen
